## **10. EVALUATION, RECORDING AND REPORTING OF AEs AND SAEs**

### **10.1 Definitions**

#### **10.1.1 Adverse Event**

Any untoward medical occurrence in a subject administered a pharmaceutical product and which does not necessarily have a causal relationship with this treatment is an AE. An AE can therefore be any unfavorable and unintended sign (including an abnormal laboratory finding), symptom, or disease temporally associated with the use of a medicinal (investigational) product, whether or not related to the medicinal (investigational) product.

#### **10.1.2 Adverse Drug Reaction**

In the pre-approval clinical experience with a new medical product or its new usages, particularly as the therapeutic dose(s) may not be established, all unintended responses to a medicinal product related to any dose should be considered adverse drug reactions (ADRs). The phrase “responses to a medicinal product” means that a causal relationship between a medicinal product and an AE is at least a reasonable possibility, i.e., the relationship cannot be ruled out.

#### **10.1.3 Serious Adverse Event**

An SAE (experience) or reaction is an untoward medical occurrence that at any dose meets one or more of the following criteria:

- Results in death (Note: death is an outcome, not an event)
- Is life-threatening (Note: the term “life-threatening” refers to an event in which the subject was at immediate risk of death at the time of the event; it does not refer to an event which could hypothetically have caused a death had it been more severe)
- Requires in-patient hospitalization or prolongation of existing hospitalization
- Results in persistent or significant disability/incapacity
- Results in a congenital anomaly/birth defect
- Is a medically important event or reaction

The definitions and reporting requirements of International Council for Harmonisation (ICH) Guidelines for Clinical Safety Data Management, Definitions, and Standards for Expedited Reporting, Topic E2 will be adhered to.

Medical and scientific judgment must be exercised in deciding whether expedited reporting is appropriate in other situations, such as important medical events that may not be immediately life-threatening or result in death or hospitalization but may jeopardize the subject or may require intervention to prevent one of the other outcomes listed in the definition above. These events will also usually be considered serious.

Hospitalizations that have been scheduled prior to the subject signing the informed consent form (ICF), although not recorded as SAEs, must be documented in the subject's source documents. A renal biopsy performed as part of the study to verify eligibility will not be considered an SAE. Any complication experienced during a renal biopsy procedure resulting in hospitalization or a prolongation of the hospitalization requires SAE reporting.

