## 4. INVESTIGATIONAL PLAN

### 4.1 Overall Study Design

This is a Phase 2, open-label, multicenter, prospective, 24-week, exploratory cohort study to assess the efficacy and safety of two dose levels of voclosporin in achieving complete or partial remission of proteinuria in subjects with biopsy-confirmed primary FSGS. Subjects who have provided a signed and dated informed consent will be screened into the study. Subjects will be assigned a unique subject number which will be used to identify them throughout the study. The duration of the screening period will be approximately 4 weeks to 10 weeks (allowing for visit windows (14±3 days) for each stability assessment) to ensure that subjects meet eligibility criteria, including renal disease stability assessments. If a subject has not had a renal biopsy within the 6-month (prior to screening) required timeframe for study eligibility, one may be performed to assess eligibility into the study, provided the subject has given consent and provided the results can be obtained and reviewed before baseline; biopsy results over 6 months prior to screening may be permitted following review with the Medical Monitor. Subjects who meet all of the inclusion criteria and none of the exclusion criteria will be eligible to receive treatment with voclosporin. Up to 10 subjects will be enrolled into Cohort 1, at a starting dose of 7.9 mg BID for Week 1, 15.8 mg BID for Week 2, and a target dose of 23.7 mg BID for Weeks 3 to 24. The first dose of study treatment should occur in the morning on Day 2, the day after dispensing. Subjects will be contacted by telephone at the end of Week 1 and Week 2 to be reminded to increase their dose as per [Section 7.1.2.1, Voclosporin Study Treatment](#).

Evaluable safety and tolerability from 12 weeks of treatment in the first 5-6 subjects from Cohort 1 are required in order to determine the dose level for Cohort 2. The dose selected may be higher or lower than 23.7 mg BID. The maximum dose possible for Cohort 2 will be 39.5 mg (5 capsules) BID. Dosing in this group will follow the same cautious approach as Cohort 1, with at a starting dose of 7.9 mg BID for Week 1, 15.8 mg BID for Week 2, 23.7 mg BID for Week 3 and a maximum dose of 39.5 mg BID for Weeks 4 to 24.

Doses and dose increments smaller than anticipated or an intermediate dose may be proposed for Cohort 2 based on the safety and tolerability results from the Cohort 1.

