If the subject is from an area where TB is endemic or whose history suggests an increased personal risk, e.g., from contact with people with TB or travel to areas with endemic TB, the subject will be carefully evaluated for latent or active TB.

Women of childbearing potential must have a negative serum pregnancy test result before baseline.

If a subject has not met the requirements in Inclusion Criteria #3 due to not having renal biopsy result within the required time frame, a renal biopsy can be performed as per local procedures, after signing the study consent, provided the results can be obtained and reviewed prior to baseline.

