## **10.3 Reporting Procedure for AEs, SAEs, and Pregnancy**

### **10.3.1 Adverse Events**

All AEs observed from time of signing of the ICF will be recorded in the subject's source documentation. This applies to all AEs regardless of presumed relationship to the study drug. For screen failure subjects, any AEs and SAEs occurring during the screening period (after informed consent) will be recorded in the subject's source documentation only and will not be collected on the eCRF. Adverse events leading to discontinuation of study drug must be collected.

If any AE is reported, the date of onset, relationship to study treatment, relationship to disease under study, any action taken, date of resolution (or the fact that it is still continuing or has become chronic), outcome, and whether the AE is serious or not, will be recorded. Use of colloquialisms and abbreviations should be avoided. Only one AE term should be recorded in the event field on the AE eCRF. Where possible, the Investigator should report a diagnosis rather than signs and symptoms or abnormal laboratory values. However, if a constellation of signs and/or symptoms cannot be medically characterized as a single diagnosis or syndrome at the time of reporting, each individual event should be recorded on the AE eCRF. If a diagnosis is subsequently established, all previously reported AEs based on signs and symptoms should be nullified and replaced by one AE report based on the single diagnosis, with a starting date that corresponds to the starting date of the first symptom of the eventual diagnosis.

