### **10.3.2 Serious Adverse Events**

For screen failure subjects, any SAEs occurring during the screening period (after informed consent) will be recorded in the subject’s source documentation only and will not be collected on the eCRF.

For enrolled subjects (i.e., those who successfully complete screening), all SAEs occurring after the signing of the ICF will be reported to [REDACTED] within 24 hours of the Investigator, designee, or site staff’s knowledge of the event regardless of relationship to study drug or relationship to disease under study. For enrolled subjects, all SAEs will be recorded in the AE section of the subject’s eCRF and source documentation.

In the event that the site experiences a temporary disruption of the EDC system a back-up paper SAE Reporting Form will be available for site staff to complete.

- Site staff will complete the paper SAE report form and e-mail it within 24 hours to the following address: [REDACTED]
- Only in cases where the email system is unavailable, site staff will send the SAE by fax to: [REDACTED].

If notification is made via email or fax, site staff must enter the SAE information into the EDC system as soon as the system becomes available.

All SAEs, regardless of causality, will be reported from the time the ICF is signed until 30 days following the last study visit or 30 days after last study treatment administration, whichever is longer. No formal study visit is required but Investigators must report any SAEs that occur during this 30-day period using the SAE reporting form provided; these will be entered into the safety database only. If the Investigator has not seen the subject at a clinic visit at the end of the reporting period, the Investigator must make reasonable efforts to contact the subject to inquire about SAEs.

All recorded SAEs, regardless of relationship to study treatment or relationship to disease under study, will be followed up until resolution, stabilization, or the subject is lost to follow-up and cannot be contacted. In circumstances where the Investigator is unable to make contact with the subject, the Investigator must provide a written statement to Aurinia confirming that the subject is lost to follow-up.

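### Serious complications of a screening biopsy in subjects who then fail screening: Section 10.1.3 requires SAE reporting, while Sections 10.3.1 and 10.3.2 keep them in source documents

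*Combined protocol and SAP*

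**What the plan says.** **The biopsy can be a study procedure.** Section 4.1 says of a subject without a recent enough biopsy that "one may be performed to assess eligibility into the study". Section 9.2.1 agrees: "a renal biopsy can be performed as per local procedures, after signing the study consent".

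**Text that requires a report.** Section 10.1.3 first excludes the procedure itself: "A renal biopsy performed as part of the study to verify eligibility will not be considered an SAE". The next sentence covers its harms: "Any complication experienced during a renal biopsy procedure resulting in hospitalization or a prolongation of the hospitalization requires SAE reporting". Neither sentence is limited to subjects who later pass screening. Section 10.3.2 also has a general rule: "All SAEs, regardless of causality, will be reported from the time the ICF is signed until 30 days following the last study visit". A cut-off tied to the last dose applies instead where it falls later.

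**Text that withholds one.** Section 10.3.2 opens by placing the screening-period SAEs of screen failures under this restriction: "source documentation only and will not be collected on the eCRF". Section 10.3.1 applies the same restriction to AEs and SAEs alike, and repeats it where it defines the AE reporting period. The 24-hour duty in Section 10.3.2 is written for enrolled subjects, glossed there as those who pass screening.

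**Related text.** Section 14.1 treats subjects as enrolled once they have signed consent. Section 13.10 plans a listing of SAEs that fall between consent and first dose. A later paragraph of Section 10.3.2 requires deaths during the study to be reported to the sponsor and does not restrict this to subjects who pass screening.

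**The concern.** A biopsy done to decide eligibility will find some subjects ineligible, and a complication may itself end a subject's screening. These subjects are screen failures, the group whose SAEs stay at the site. A site that follows the screen-failure rule would not send the sponsor a serious injury from a procedure performed under the protocol, although Section 10.1.3 says such an injury must be reported.

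What is at stake is the sponsor's knowledge of procedural harm, not any efficacy result. The study has no data and safety monitoring board (Section 12), so no independent board is in place to notice the omission. The pre-dose SAE listing could also look complete while lacking these events.

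**Working it through.** The plan states no figure on this point, so the check sets the rules side by side and applies them case by case.

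**Rules**
- A (10.1.3): a biopsy complication that causes or prolongs hospitalization needs SAE reporting.
- B (10.3.1, stated twice, and 10.3.2): SAEs of screen failures are recorded in source documents only.
- C (10.3.2): 24-hour reporting for subjects who pass screening.
- D (10.3.2): all SAEs are reported from consent.
- E (10.3.2): deaths during the study are reported to the sponsor.

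**Cases**

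| Case | Rules that call for a report | Rules against | Result |
|---|---|---|---|
| 1. Screening biopsy, hospitalised complication, subject passes screening | A, C, D | none | reported |
| 2. Week 24 repeat biopsy, hospitalised complication | A, C, D | none | reported |
| 3. Screening biopsy, hospitalised non-fatal complication, subject fails screening | A, D | B; C does not apply | contradiction |
| 4. As case 3, but fatal | A, D, E | B | a route to the sponsor exists, though B still conflicts |

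Case 3 is the gap. A and D cannot both be followed together with B.

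**Timing.** The 24-hour clock starts when site staff learn of the event. Screening lasts about 4 to 10 weeks (Section 9.2.1), that is 4 × 7 = 28 to 10 × 7 = 70 days. Unless the complication itself settles eligibility, the site may have to act within 1 day on a status not fixed until weeks later. If it reports at once and the subject then fails, it has departed from B. If it waits and the subject then passes, it has missed the deadline in C.

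**Meaning of enrolled.** Under Section 10.3.2 no screen failure is enrolled. Under Section 14.1 every consented subject is. The second meaning would bring case 3 under the 24-hour duty, but Section 10.3.2 gives its own gloss, which excludes it.

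**Route.** The normal route in Section 10.3.2 is the EDC system. The paper form is a back-up for outages and must be entered in EDC afterwards. B keeps case 3 off the eCRF. The section does provide for entry in the safety database alone, but for SAEs in the 30-day period after the end of participation.

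**Listing.** Section 13.10 does not name its data source or say whether screen failures are included. If the listing is drawn from eCRF data, case 3 events cannot appear in it.

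**The case against.** The strongest reply is that Section 10.1.3 is the specific rule. It deals with biopsy complications directly, straight after the sentence on the eligibility biopsy, and the sentence requiring all SAEs from consent supports it. A careful site could report on that basis. This stands in part: reporting in case 3 is possible, and the omission is not certain. It does not settle the matter, because the screen-failure rule is just as explicit, appears three times, and makes no exception for harm from a study procedure. Each side can claim to be the specific rule.

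A reader might infer something stronger: that the protocol leaves screen failures with no route to the sponsor, so that every such event is lost. The documents do not support this. The general SAE sentence has no screen-failure exception, deaths are covered separately, and paper forms and safety-database-only entry exist for other situations. Nor can any percentage be given, since the documents state no number of screening biopsies, complication rate or screen-failure rate.

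Three further points hold and limit the weight of the concern:
- The screening biopsy is optional, and older biopsies may be accepted after review with the Medical Monitor.
- Screen failures receive no voclosporin and are outside the ITT and safety sets, so no remission rate, confidence interval or TEAE table changes, and the Cohort 2 dose decision is unaffected.
- The event remains in source documents, which are open to monitoring.

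Keeping screen-failure data to a minimum may well be deliberate. But Section 10.1.3 shows that reports of biopsy complications were intended, and the later sections can defeat that.

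**Conclusion.** The protocol contradicts itself for one defined case: a non-fatal, hospitalised complication of a study screening biopsy in a subject who then fails screening. Such an event can go unreported to the sponsor. Its absence from the pre-dose SAE listing follows only if that listing is built from eCRF data, which is an assumption.

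The case needs four things together: a study biopsy during screening, a complication with hospitalization, survival, and screen failure. With about 20 subjects planned, the number is probably small, though screen failures come on top of those 20 and the documents do not say how many are expected. The conclusion does not depend on the count. A site that follows Sections 10.3.1 and 10.3.2 as written would withhold safety information that Section 10.1.3 requires. The text should be corrected, and no change to the design or the analysis is needed.

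**What to change.** Reconcile Sections 10.1.3, 10.3.1, 10.3.2, 13.10 and 14.1:

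1. State in 10.3.1 and 10.3.2 that an SAE related to a protocol procedure, including the screening biopsy, in any consented subject is reported to the sponsor's safety database within 24 hours of site awareness, whatever the screening outcome.
2. Amend every statement of the source-only rule, including both in 10.3.1, to carry this exception. Make the general sentence on all SAEs from consent agree with it, so that it is clear which other screen-failure SAEs, if any, are reported.
3. Name the reporting route for subjects without an SAE record on the eCRF. Entry in the safety database alone, already used for the 30-day period, would serve.
4. Use one definition of enrolled in 10.3.2 and 14.1.
5. State in 13.10 that the pre-dose SAE listing includes these events, and from which database they are taken.
6. Ask the investigator to judge relationship to a study procedure. The AE attributes in 10.3.1 cover only relationship to study treatment and to the disease.

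The cost is a few sentences in an amendment and a few extra SAE forms. Reconciling the safety database with the listing adds a small task at reporting.

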#### **10.1.4 Suspected Unexpected Serious Adverse Reaction**

Any ADR that is both serious and unexpected (per the IB) that, based on the opinion of the Investigator or Aurinia, is felt to have a reasonable suspected causal relationship to a medicinal product is a suspected unexpected serious adverse reaction.

### **10.2 Adverse Event Descriptors**

#### **10.2.1 Intensity/Severity Categorization**

The term "severe" is often used to describe the intensity (severity) of a specific event (as in mild, moderate, or severe myocardial infarction); however, the event itself may be of relatively minor medical significance (such as severe headache). This is not the same as "serious," which is based on subject/event outcome or action criteria usually associated with events that pose a threat to a subject's life or ability to function. Seriousness (not severity) serves as a guide for defining regulatory reporting obligations.

In general, the intensity of a particular AE to be recorded is the worst intensity experienced by the subject during the course of the event. The medical assessment of intensity will be determined by using the following definitions:

Mild: The AE is easily tolerated and does not interfere with usual activity.

Moderate: The AE interferes with daily activity, but the subject is still able to function.

Severe: The AE is incapacitating and the subject is unable to work or complete usual activity.

#### **10.2.2 Causal Relationship Categorization**

An Investigator who is qualified in medicine must make the determination of relationship to the study treatment for each AE and SAE. The Investigator must decide whether, in his or her medical judgment, there is a reasonable possibility that the event may have been caused by the

study treatment. If there is no valid reason for suggesting a relationship, then the AE/SAE must be classified as not related. Otherwise, if there is any valid reason, even if undetermined or untested, for suspecting a cause-and-effect relationship between the study treatment and the occurrence of the AE/SAE, then the AE/SAE will be considered related. For SAEs, the Investigator must provide a brief comment explaining the rationale of his/her assessment of causal relationship on the SAE reporting form.

The following additional guidance may be helpful:

Term	Relationship	Definition
Related	Yes	The temporal relationship of the clinical event to study treatment administration indicates a causal relationship, and other drugs, therapeutic interventions or underlying conditions do not provide a sufficient explanation for the observed event.
Not related	No	The temporal relationship of the clinical event to study treatment administration does not indicate a causal relationship, or other drugs, therapeutic interventions or underlying conditions provide a sufficient explanation for the observed event.

If the causal relationship between an AE/SAE and the study treatment is determined to be “related”, the event will be considered to be related to study treatment for the purposes of expedited regulatory reporting. In circumstances where the Investigator has not yet provided his/her assessment about the relationship, the event will be considered as “related” and qualify for expedited regulatory reporting.

### **10.2.3 Outcome Categorization**

Outcome may be classified as recovered without sequelae; recovered with sequelae; improved; worsened; ongoing; ongoing at end of study; fatal; or unknown. If the outcome is reported as recovered with sequelae for an SAE, the Investigator should specify the kind of sequelae on the SAE reporting form. SAEs that are ongoing at the time of death will have an outcome of “unknown” recorded. SAEs resulting in a fatal outcome will have an outcome of “fatal” recorded.

### **10.2.4 Clinical Laboratory Evaluations**

A change in the value of a safety laboratory investigation can represent an AE if the change is clinically relevant in the opinion of the Investigator or if, during treatment with the study treatment, a shift of a parameter is observed from a normal value to a pathological value, or a further worsening of an already pathological value.

If, at the end of the treatment phase, there are pathological laboratory values which were not present at baseline, further clinical or laboratory investigations will be performed until the values return to within reference range or until a plausible explanation (e.g., concomitant disease) is found for the pathological laboratory values.

If the Investigator considers such an AE as serious it must be reported as an SAE.

### **10.2.5 Abuse, Misuse, Overdose and Medication Error**

All AEs of special interest such as study drug abuse, misuse, overdose, and medication error have to be documented in the subject's eCRF and source documentation. If any occurrence of abuse, misuse, overdose, or medication errors leads to any event that fulfils any seriousness criteria, the event has to be reported as an SAE.

## **10.3 Reporting Procedure for AEs, SAEs, and Pregnancy**

### **10.3.1 Adverse Events**

All AEs observed from time of signing of the ICF will be recorded in the subject's source documentation. This applies to all AEs regardless of presumed relationship to the study drug. For screen failure subjects, any AEs and SAEs occurring during the screening period (after informed consent) will be recorded in the subject's source documentation only and will not be collected on the eCRF. Adverse events leading to discontinuation of study drug must be collected.

If any AE is reported, the date of onset, relationship to study treatment, relationship to disease under study, any action taken, date of resolution (or the fact that it is still continuing or has become chronic), outcome, and whether the AE is serious or not, will be recorded. Use of colloquialisms and abbreviations should be avoided. Only one AE term should be recorded in the event field on the AE eCRF. Where possible, the Investigator should report a diagnosis rather than signs and symptoms or abnormal laboratory values. However, if a constellation of signs and/or symptoms cannot be medically characterized as a single diagnosis or syndrome at the time of reporting, each individual event should be recorded on the AE eCRF. If a diagnosis is subsequently established, all previously reported AEs based on signs and symptoms should be nullified and replaced by one AE report based on the single diagnosis, with a starting date that corresponds to the starting date of the first symptom of the eventual diagnosis.

The AE reporting period begins at the time the ICF is signed by the subject. Note that for screen failure subjects, any AEs and SAEs occurring during the screening period will be recorded in the subject's source documentation only. For enrolled subjects (i.e., those who successfully complete screening), the AE reporting period ends at the second Safety Follow-up visit (Visit 10). Adverse events persisting at the time of study completion will be followed by the Investigator through contact with the subject until resolution or stabilization has occurred (or the subject is lost to follow-up and cannot be contacted) and recorded in the source documents. If the subject reports an AE, it is the Investigator's responsibility to acquire sufficient information in order to assess causality. This may require additional laboratory testing, physical examinations, telephone contacts, etc. In circumstances where the Investigator is unable to make contact with the subject, the Investigator must provide a written statement to Aurinia confirming that the subject is lost to follow-up.

In order to avoid bias in eliciting AEs, subjects should be asked a non-leading question, such as “How are you feeling?” It is also important to question the subject in a non-leading way about changes in their health or concomitant medication usage since their last visit. This information should be collected prior to completion of assessments at all study visits. In addition, any symptoms/conditions reported during assessments and deemed to be clinically significant by the Investigator will be considered AEs.

